## D.2 Inclusion/Exclusion Criteria for R61 and R33

Inclusion: 1) SCID-5 diagnosis of schizophrenia; 2) 18-60 years old; 3) speaks English; 4) able to complete the MATRICS Consensus Cognitive Battery (MCCB) at the baseline assessment (for R33); 5) a raw score of 37 or greater on the Wide Range Achievement Test, Reading subtest (WRAT-3), to establish a minimum reading level (6th grade) and to estimate premorbid IQ; and 6) clinically stable as indicated by no antipsychotic medication changes in the last month or if on depot, no change in the past 2 months. Exclusion: 1) history of intellectual disability, or developmental or neurological disorder; 2) history of brain trauma associated with loss of consciousness for > 10 minutes or behavioral sequelae; 3) alcohol or substance use disorder within the last 6 months; and 4) history of eye disease (e.g., glaucoma, retinopathy). Effects of tobacco use and medication dose equivalents, including an index of anticholinergic load, will be explored in data analyses.

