# D.3 R61 Phase

Aims: (i) To evaluate the effects of UE and CIT on the CS and PO targets, respectively; (ii) to determine if the criterion for continuing to the R33 phase is met; and (iii) if the criterion is met, to determine the most effective intervention condition and optimal duration of treatment, to inform the R33 study design.

Study design: 80 subjects will be enrolled in this study: 20 per arm. 40 will be recruited at each site (Rutgers and NKI). The intervention will continue for 40 sessions, with targets assessed before training, after every 10 sessions, and at 6 months post-training for a total of 6 visual assessments. With 3 sessions per week, the intervention will take between 13-14 weeks. Each site will enroll ~ 2 participants/month, beginning after the first half of Y1, which is similar to what Keefe et al. estimated as a "reasonable rate of recruitment for a largescale efficacy trial" of cognitive remediation. Because, at the 6-month follow-up, nearly all patients are expected to still be in the partial hospital program, or an outpatient program (at Rutgers), or on inpatient units at the Rockland Psychiatric Center (RPC) or NKI, we expect attrition to be minimal. However, several methods, including monthly phone calls (see Recruitment and Study Timeline), will be used to maximize retention. For the R61 and R33, training sessions will be run in small groups by front-line staff who have already received training in these interventions, or whom we will train, with no more than a 3:1 participant:staff ratio. Randomization: Subjects will be randomly assigned, within site, to one of the 4 conditions (UE&ACCT, CIT&ACCT, UE&CIT and ACCT&ACCT) in a ratio of 1:1:1:1. The treatment assignment will be made after a subject has met all entry criteria and completed baseline testing, to avoid bias.

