is similar to that observed in many studies of cognitive remediation, and of other treatments for this population, such as skills training and family psycho-education. However, less is known about effect sizes of perceptual remediation, and most of the evidence on this in schizophrenia comes from studies of auditory remediation using the Posit Science auditory training module, which includes training on both low-level auditory targets and higher-level auditory-verbal cognition (e.g., verbal working memory and learning). Results from one study indicated an improvement in the target of auditory-processing speed that was of large effect (d=0.875). The authors also observed a medium-large effect on global cognition (d=0.73). Results from other studies of this auditory training module in schizophrenia have indicated large treatment effects (d=0.86) for both verbal learning and global cognition, and a medium effect (d=~0.65) on the auditory target of P50 gating. While these effect sizes are larger than our chosen criterion (d=.4), it is also important to note that some studies of Posit Science modules have not demonstrated significant improvement on non-trained tasks. Moreover, across studies, the largest effects have tended to come from studies where daily training (5 days a week) was used, and subjects were paid for completing training sessions, and these are two conditions that can rarely be met in real world psychiatric clinics. These considerations have informed our choice of the 'go signal' criterion (i.e., d=.4), because there are as of yet very few published studies of visual remediation in schizophrenia. One small (N=9) uncontrolled study of visual backward masking training found an effect size of d=.43 for improvement in the MATRICS domain of Visual Learning. Within our group, [name] observed an improvement in contour integration performance among participants with schizophrenia after 4 consecutive days of practice on a contour integration task (phi=0.63, which corresponds to a large effect). Even larger effect sizes were seen for changes in CS (d=0.96), and PO (d=0.85) in our small pilot sample of patients with schizophrenia (Section D1), but given the small sample size and lack of a control group in that study it can be assumed that the real effect size is lower. Thus, findings from these initial evaluations of visual remediation support our use of d=0.4 as a conservative level of change on the outcome measures and as a "go" signal for target engagement. However, we acknowledge that it is not yet clear from the literature how an effect of this size relates to meaningful improvements in visual and higher-order cognitive processing, and/or functional capacity. The proposed R33 will allow us to address this guestion in a preliminary manner. If results from this trial are positive, we will seek funding for a larger trial to evaluate the impact of this treatment on functional outcomes, and to identify mediators/moderators of treatment response. If the Go criterion is met for any of the treatment conditions, we will perform a thorough investigation of the effects of UE, CIT, and UE&CIT on the CS and PO target scores to determine which remediation strategy to use for the R33. Analyses will also include (i) assessment of the trajectory of performance on the target measures over the course of treatment; (ii) determinations of whether the improvements plateau prior to the 40th session or whether they continue throughout the training period; and (iii) evaluations of whether any combined effects of UE and CIT are additive or multiplicative. These goals will be accomplished by first graphically examining the trajectories of target change to assess whether they are linear, monotonic non-linear, guadratic, or any other shape. After that, appropriate models for longitudinal data analysis will be applied to estimate improvement rate and time to asymptote. We will account for CPZ-equivalent dose of antipsychotic medications in all models, using CPZ dose as a time-varying covariate if necessary, and will also account for type of antipsychotic medication and anticholinergic load. Those models will also be used to examine whether baseline characteristics moderate the effect of UE and/or CIT on the targets. These analyses will allow us to ascertain: 1) whether UE alone, by targeting CS function, has a cascading effect on PO; 2) whether CIT improves CS while targeting PO function; and 3) whether UE&CIT has a stronger effect than either intervention alone for any outcome. Based on these results, the optimal intervention will be determined based on it having a significantly larger effect size for at least one target. If all 3 treatment conditions are effective to an equivalent degree, the criterion will be reaching asymptotic level of improvement earliest.

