Aims: (i) To replicate and extend R61 results supporting initial visual target engagement using the optimal R61 treatment, in a new and larger sample; and (ii) to determine if visual target engagement is associated with improvements in specific cognitive (i.e., visual working memory, visual learning and memory, reading) and social cognitive (*i.e.*, facial emotion recognition) outcomes, as well as with changes in functional capacity. Study design: The R33 will be a two parallel-arm RCT comparing the optimal R61 treatment to the control (ACCT) treatment. 100 subjects will be enrolled over 3 years, 50 from NKI and 50 from Rutgers. Visual and clinical outcome assessments will be conducted at baseline, and at intervals determined based on R61 results, including a 6-month follow-up (with attrition considerations and procedures identical to the R61 (see D.3). **Randomization:** Subjects will be randomly assigned, within site, to the optimal or control treatment in a ratio of 1:1. Treatment assignment for eligible subjects will occur after completion of baseline testing, to avoid bias. Assessments: Visual Targets and Cognitive, Social Cognitive, and Functional Capacity. No matter which intervention is used for the R33, visual tests will include both tests of CS, and both tests of PO used in the R61. See below (section D.6.c) for descriptions of the cognitive, social cognitive, and functional capacity measures. **Data analysis:** An intention to treat approach to data analysis will be used in this clinical trial. For all analyses. statistical significance will be defined as p < 0.05, unless specified otherwise. Bonferroni corrections will be applied to multiple testing, as appropriate. H1: The optimal R61 treatment will be more effective than the control treatment (ACCT) in improving CS and/or PO test scores (to be determined based on the R61 outcome). This will be tested using a linear mixed effects model in which the values of the target(s) at each time point are modeled as a function of treatment group (experimental, control), time, time x group, and potential moderators and mediators (e.g., age). We will use Akaike's Information Criterion (AIC) as the deciding metric to determine the optimal model to account for within-subject correlations between repeated measures (e.g., autoregressive of order 1, AR(1), which assumes stronger within-person correlation for measurements closer in time, or other structures). If the time x group interaction is significant, we will use model-based estimation procedures to estimate the magnitude of the effect. We will also explore differential effects of the treatment on CS vs. PO. H2: Improvements in visual processing, as observed in CS and/or PO (based on R61 results), will be related to changes on specific cognitive (i.e., visual working memory, visual learning and memory, reading), social cognitive (i.e., emotion recognition), and functional capacity measures. We will assess correlations between visual target scores and cognition, social cognition, and functional capacity, and also evaluate whether changes in the target(s) either mediate or moderate treatment effects on these outcomes. An approach and computational tool described by Hayes will be used to model any mediation and /or moderation effects, including indirect effects in models that involve mediation. Sample size determination: The sample size for the RCT in the R33 phase was selected to ensure sufficient power to detect medium effects of the experimental intervention on the target(s). For Aim 1 of the R33, 50 subjects per condition allows 80% power for a 2-tailed test with  $\alpha$ =0.05 to detect d=0.57. For Aim 2, with n=50 in the active perceptual training group, correlations of at least r=0.38 between changes in performance on target measures (CS and/or PO) and changes in cognitive, social cognitive, and functional capacity can be detected with 80% power using a 2-tailed test with  $\alpha$ =0.05. Also, for Aim 2, n=50 (i.e., active perceptual intervention only) allows for detecting a correlation of r=0.43 when making a strict Bonferroni adjustment for 3 outcomes (2-tailed  $\alpha$ =0.017), and r=0.51 when correcting for 15 outcomes (2-tailed  $\alpha$ =0.003). In accordance with instructions that the R33 "should not be powered as a strong test of clinical efficacy...", our focus on effect size is exploratory and not confirmatory. We will use our observed effect sizes to power a later RCT. D.5 Interventions

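### The R61 models that choose the R33 treatment may adjust the arm effect for antipsychotic dose recorded after randomisation, and R33 H1 admits mediators into the test of treatment effect

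*Combined protocol and SAP*

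**What the plan says.** Section D.3 (R61 Phase) provides that, once the Go criterion is met, the effects of UE, CIT and UE&CIT on the targets will be investigated "to determine which remediation strategy to use for the R33". The rule is that "the optimal intervention will be determined based on it having a significantly larger effect size for at least one target". If all three are equally effective, the one that reaches its asymptote first is taken.

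On covariates for these models, D.3 states: "We will account for CPZ-equivalent dose of antipsychotic medications in all models, using CPZ dose as a time-varying covariate if necessary". It adds that the analysis "will also account for type of antipsychotic medication and anticholinergic load". The trigger for the time-varying form is not defined, and neither drug type nor anticholinergic load is tied to a time of measurement. Baseline is mentioned nearby only for moderation: "Those models will also be used to examine whether baseline characteristics moderate the effect of UE and/or CIT on the targets".

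Three other provisions fix the timing:
- Randomisation (D.3): "The treatment assignment will be made after a subject has met all entry criteria and completed baseline testing".
- Medication stability (D.2) is an entry condition only: "clinically stable as indicated by no antipsychotic medication changes in the last month", with a longer window for depot drugs.
- Targets are assessed at baseline, after every 10 of the 40 sessions (13 to 14 weeks in all), and 6 months after training (D.3).

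For the R33, the data-analysis text in D.4 tests H1 with a mixed model whose terms include "time x group, and potential moderators and mediators (e.g., age"). Mediation is also planned under H2 in the same section.

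**The concern.** Randomisation makes the arms comparable on everything fixed before assignment. It does not do so for dose recorded later. If a training programme changes clinical state, and clinical state changes prescribing, then current dose is partly a consequence of arm. Holding it constant removes whatever part of the training effect runs through dose. It also links arm to any unmeasured clinical state that drives both dose and visual performance. The arm coefficient then answers a different question from the one the selection step asks.

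The documents do not show that arm affects dose, but they give reasons not to assume independence. The control programme includes emotion regulation and goal-setting components (D.5), and its share differs by arm: both halves of training in ACCT&ACCT, one half in UE&ACCT and CIT&ACCT, none in UE&CIT. Section B also links gain control, the function UE trains, to hallucination risk.

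At stake is which treatment, at which duration, enters a 100-person second phase. In the R33 the stake is the H1 test itself: a true mediator entered as a covariate takes out the part of the treatment effect that it carries.

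**Working it through.** **Is the covariate restricted anywhere?** No section limits CPZ-equivalent dose to its baseline value, names a model without on-study dose as the main one, or labels the time-varying version a sensitivity analysis. The obvious reason to find the time-varying form necessary is that doses changed on study, which is exactly when the covariate is post-randomisation.

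**How would bias arise?** The plan states no figure to reproduce, so the following is an illustration. Every value of a, b, c and g is an assumption; the documents give none. Take arm A (0/1), on-study dose M with within-arm SD 1, latent clinical state U, and target change Y in SD units:

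- M = aA + gU + error
- Y = (τ − ab)A + bM + cU + error, so the total arm effect is τ.

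Given A and M, the expected value of U is g(M − aA). Substituting, the coefficient of A in a model containing M is τ − ab − acg. Hence

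bias = −a(b + cg).

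With τ = 0.40, the dose-adjusted arm effect is:

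| a (arm effect on dose, SD) | b=0, c=−0.3, g=0.5: b+cg=−0.15 | b=−0.2, c=0, g=0: b+cg=−0.20 | b=−0.2, c=−0.3, g=0.5: b+cg=−0.35 |
|---|---|---|---|
| 0 | 0.400 | 0.400 | 0.400 |
| −0.1 | 0.385 | 0.380 | 0.365 |
| −0.2 | 0.370 | 0.360 | 0.330 |
| −0.4 | 0.340 | 0.320 | 0.260 |

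For the last cell: −(−0.4) × (−0.35) = −0.14, and 0.40 − 0.14 = 0.26. A simulation with 400,000 subjects per scenario agreed with the formula to about 0.001. Without the dose term, the arm coefficient recovers 0.40. The sign is not fixed: with a = +0.2 and b + cg = −0.35 the shift is +0.07, giving 0.47.

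**Effect on the ranking.** With common slopes, the contrast between active arms j and k shifts by −(a_j − a_k)(b + cg). This is zero when both arms affect dose equally. If one arm had a = −0.4 and another a = 0, with b + cg = −0.35, two equal true effects of 0.40 would appear as 0.26 and 0.40. For scale, the standard error of a two-arm difference at 20 per arm is √(2/20) = 0.316 SD, so that gap is 0.14/0.316 = 0.44 standard errors.

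**Chance imbalance is a different matter.** If a = 0 but the arms happen to differ in dose by 0.3 SD, the unadjusted estimate is off by (b + cg) × 0.3, for example −0.35 × 0.3 = −0.105. The adjusted estimate stays centred on 0.40. Only an effect of arm on dose creates the bias.

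**R33 H1.** CPZ dose is not named in this model. The issue there is only the word mediators among the terms of the model that tests the time-by-group interaction.

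**The case against.** The strongest reply is that bias needs training to change dosing, and nothing in the documents shows that it does. Most participants are expected to be long-stay inpatients or partial hospital patients, medication is stable at entry, and all conditions are designed to be similarly engaging. The time-varying form is conditional. The result of the selection step is re-tested in a new randomised sample. Dose adjustment can also help: it corrects a chance imbalance in dose, and it can explain a within-person shift in performance after a dose change, which is relevant when trajectories and plateaus are being described.

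Most of this stands as a limit on size. It does not settle the point, because the plan neither establishes independence of arm and dose nor defines when the time-varying form applies. That choice could therefore be made after the data are seen. Re-testing in the R33 would show whether the chosen treatment works; it would not recover a better arm that had been passed over.

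On the R33, the only example given for the extra H1 terms is age, a baseline variable that cannot be a mediator, so the phrase may simply be loose. It still permits what it says.

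**Conclusion.** The point holds as a risk that the plan leaves open, and it should be corrected. As written, the arm effects that choose the R33 treatment and duration can be conditioned on a post-randomisation variable. The size and direction are unknown. The 0.26 to 0.385 range against a true 0.40 rests on assumed values in a simplified single-dose linear model, and the bias is zero if arm does not affect dose.

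A reader might infer more than the documents support:
- **That the Go decision is compromised.** It is not. D.3 bases it on raw pre-post change scores and mentions no medication covariate.
- **That a chance dose difference at 20 per arm biases the adjusted effect.** It does not, as shown above.
- **That treating clinicians know the arm and prescribe accordingly.** The documents do not say so.
- **That the selection is certain to be distorted.** The ranking can change only if the bias differs between active arms.
- **That R33 H1 repeats the dose adjustment.** D.4 does not name dose in that model; D.2 says only that medication effects will be explored.

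**What to change.** For the R61 selection models in D.3:
- adjust for baseline CPZ-equivalent dose, baseline antipsychotic type and baseline anticholinergic load only;
- state that outcomes are used regardless of later medication changes;
- tabulate on-study medication changes by arm;
- report a model with time-varying dose only as a labelled sensitivity analysis.

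For R33 H1 in D.4, delete mediators from the model terms, restrict covariates to pre-randomisation variables, and leave mediation to H2.

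These are changes to analysis wording, with no added participants or visits, and they do not bear on how medication is managed. There is one small cost: the main R61 model will not explain within-person shifts in performance that follow a later dose change. The sensitivity analysis covers that.

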# Sample size determination:

The sample size of the R61 study (n=20/group) was selected to ensure that when the true size of the effect of UE or UE&CIT on the CS target, or CIT or UE&CIT on the PO target, is d=0.4, the 95% confidence interval (CI) for the effect size does not contain zero. Given data on the CS measure over time in the UE pilot study described earlier, a 95% confidence interval for an effect size of magnitude 0.4 is between .02 and .91. Since the observed effect size in that pilot data was actually much larger, 0.96, we are confident that we will be adequately powered to detect a meaningful effect. Since patients also improved on a measure of contour integration (d=0.85) in the pilot study, even though training was focused only on CS (our low-level visual target), setting the effect size at d=0.4 for both CS and PO seems reasonable. Note that although contour integration improved without PO training in the pilot study, this was unlikely due to practice effects on the test alone since two prior large studies did not find practice effects on the JOVI, in either healthy controls or

patients, over two or three repeated presentations separated by days or weeks, and a third study found improvements only with daily exposure to two versions of the task, and this did not occur for the schizophrenia group until the third day. Subjects who do not complete all 40 sessions of training will be invited to complete a "post-treatment" assessment after their last session; for non-completers who decline to participate in a post-treatment evaluation, the last post-baseline assessment will be used, unless the participant dropped out before the 10th session (the time of 1st post-baseline assessment), in which case his/her data will be not be used in the analyses. In such cases, we will recruit additional participants to reach the target sample size. We expect minimal dropout since most participants will be long-stay inpatients or partial hospital patients who are present on a nearly daily basis. For any dropout that does occur, we expect rates to be uniform across conditions, given that we have designed all conditions, including the active control, to be similarly engaging. Sufficient patients are available at both sites to recruit new subjects to replace any who discontinue. D.4 R33 Phase

[figure not shown]
Aims: (i) To replicate and extend R61 results supporting initial visual target engagement using the optimal R61 treatment, in a new and larger sample; and (ii) to determine if visual target engagement is associated with improvements in specific cognitive (i.e., visual working memory, visual learning and memory, reading) and social cognitive (*i.e.*, facial emotion recognition) outcomes, as well as with changes in functional capacity. Study design: The R33 will be a two parallel-arm RCT comparing the optimal R61 treatment to the control (ACCT) treatment. 100 subjects will be enrolled over 3 years, 50 from NKI and 50 from Rutgers. Visual and clinical outcome assessments will be conducted at baseline, and at intervals determined based on R61 results, including a 6-month follow-up (with attrition considerations and procedures identical to the R61 (see D.3). **Randomization:** Subjects will be randomly assigned, within site, to the optimal or control treatment in a ratio of 1:1. Treatment assignment for eligible subjects will occur after completion of baseline testing, to avoid bias. Assessments: Visual Targets and Cognitive, Social Cognitive, and Functional Capacity. No matter which intervention is used for the R33, visual tests will include both tests of CS, and both tests of PO used in the R61. See below (section D.6.c) for descriptions of the cognitive, social cognitive, and functional capacity measures. **Data analysis:** An intention to treat approach to data analysis will be used in this clinical trial. For all analyses. statistical significance will be defined as p < 0.05, unless specified otherwise. Bonferroni corrections will be applied to multiple testing, as appropriate. H1: The optimal R61 treatment will be more effective than the control treatment (ACCT) in improving CS and/or PO test scores (to be determined based on the R61 outcome). This will be tested using a linear mixed effects model in which the values of the target(s) at each time point are modeled as a function of treatment group (experimental, control), time, time x group, and potential moderators and mediators (e.g., age). We will use Akaike's Information Criterion (AIC) as the deciding metric to determine the optimal model to account for within-subject correlations between repeated measures (e.g., autoregressive of order 1, AR(1), which assumes stronger within-person correlation for measurements closer in time, or other structures). If the time x group interaction is significant, we will use model-based estimation procedures to estimate the magnitude of the effect. We will also explore differential effects of the treatment on CS vs. PO. H2: Improvements in visual processing, as observed in CS and/or PO (based on R61 results), will be related to changes on specific cognitive (i.e., visual working memory, visual learning and memory, reading), social cognitive (i.e., emotion recognition), and functional capacity measures. We will assess correlations between visual target scores and cognition, social cognition, and functional capacity, and also evaluate whether changes in the target(s) either mediate or moderate treatment effects on these outcomes. An approach and computational tool described by Hayes will be used to model any mediation and /or moderation effects, including indirect effects in models that involve mediation. Sample size determination: The sample size for the RCT in the R33 phase was selected to ensure sufficient power to detect medium effects of the experimental intervention on the target(s). For Aim 1 of the R33, 50 subjects per condition allows 80% power for a 2-tailed test with  $\alpha$ =0.05 to detect d=0.57. For Aim 2, with n=50 in the active perceptual training group, correlations of at least r=0.38 between changes in performance on target measures (CS and/or PO) and changes in cognitive, social cognitive, and functional capacity can be detected with 80% power using a 2-tailed test with  $\alpha$ =0.05. Also, for Aim 2, n=50 (i.e., active perceptual intervention only) allows for detecting a correlation of r=0.43 when making a strict Bonferroni adjustment for 3 outcomes (2-tailed  $\alpha$ =0.017), and r=0.51 when correcting for 15 outcomes (2-tailed  $\alpha$ =0.003). In accordance with instructions that the R33 "should not be powered as a strong test of clinical efficacy...", our focus on effect size is exploratory and not confirmatory. We will use our observed effect sizes to power a later RCT. D.5 Interventions

ULTIMEYES (UE) Training: The UE training procedure was developed by [name] and colleagues at UCR. The program uses video game-based custom software, and the training stimuli consist of Gabor patches (game "targets") at 6 SFs (1, 2, 4, 8, 16 and 32 cycles/degree), and 8 orientations (22.5°- 337.5°). We describe this program as a "video-game" because numerous elements were introduced to its design with the goal of promoting task engagement and user enjoyment. For instance, points are given each time a target is selected (and taken away when distractors are selected), and levels increase in difficulty throughout training. At the beginning of each session a calibration is run to determine the initial contrast values for each SF to be displayed during the training exercises. Each session consists of 8-12 training exercises that last

approximately 2 minutes each for a total of ~25 min. The participant's task is to click on all the Gabor targets as quickly as possible. The first few exercises consist of only targets, but distractors are added as the training progresses (Fig. 2). Throughout training, distractors become more similar to the targets (starting off as blobs, then oriented patterns, then noise patches of the same SF as the targets). Targets that are not selected in time start flickering at a 20-Hz frequency, to attract attention. At higher levels, targets and distractors appear and disappear when not selected quickly enough. Many parameters are adjusted based on ongoing participant performance, including contrast (using a 3/1 staircase for each SF), number of stimuli per trial, and

presentation rate (determined by tracking average response times on prior trials for each SF). **Contour Integration Training (CIT):** The CIT program was developed by co-investigator [name] and is based largely on two contour integration tasks we developed and have used in multiple studies of visual PO in schizophrenia . There are two PO exercises used for this program, which are presented in alternating blocks

of individual trials. Target stimuli in both exercises consist of contours that are formed by fragmented paths of individual Gabor elements, which are embedded within an array of noise Gabors. For one of the exercises, the participant's task is to detect and click on the circular contour formed by a set of target Gabors. Difficulty level is manipulated by varying the degree of orientational jitter of the Gabors making up the target contour (see Fig. 3), which is done within block, and by varying the number of elements that make up the circle, which is done between blocks. The degree of jitter is determined adaptively using a '3 up, 1 down' staircase at steps of 1 degree; jitter values and element density were chosen based on data from multiple previous studies with patients and controls. For the other exercise, orientational and positional jitter of contour elements are systematically added to increase task difficulty over time. In addition, several basic discriminations will be included to

promote generalization, including those involving shapes (e.g., circles vs. ellipses) and numbers (e.g., '2' vs. '5'). For both exercises, the arrays of Gabor elements have a peak SF of 4 cycles/degree (to eliminate potential effects related to impairments in processing LSFs) and a Gaussian envelope SD of 7.3 arcmin. Like UE, CIT is presented as a game: Participants are provided with feedback about their response accuracy, points are given for each correct response, and positive feedback is provided when participants progress to the next difficulty level. This program also uses a staircase procedure to automatically adjust the current difficulty level based on recent performance so that it becomes more challenging as performance improves; this feature is designed to drive performance gains, and to continuously challenge participants while ensuring continued success. Each session consists of 8-12 training exercises that last approximately 2 minutes, for a total of ~25 min. Active Computer-Based Control Treatment (ACCT): Our control condition is a cognitively challenging remediation program that does not specifically target perception. MyBrainSolutions (MBS; Brain Resource, Inc.) is a suite of online games and exercises targeting the domains of: 1) cognition (attention and memory); 2) emotion regulation (using imagery, and breathing rate-based biofeedback); and 3) goal setting and attainment (using individualized goals, reminders, feedback, and problem solving suggestions). It has been used extensively in workplace settings and via the internet to promote wellness and employee productivity. [name] has previously used MBS clinically for cognitive remediation of patients with psychosis since 2010.

